5.5 Duration of Study Participation

Pre-operative visit will occur up to 3 months prior to surgery. Final Study visit will occur up to 6 weeks after surgery. Primary endpoint (returning completed pain diary to study staff) occurs at Day 14. Participants

CONFIDENTIAL

This material is the property of the NYU School of Medicine and Langone Medical Center. Do not disclose or use except as authorized in writing by the study sponsor
Interventional Template Version: 11 January 2019

remain enrolled in the study up until their standard of care post-op visit, which typically occurs 4-6 weeks after surgery. Participation is complete when participants complete their final standard of care post-op visit.

5.6 Total Number of Participants and Sites

Patients will be recruited from NYU Langone Health and from Bellevue Hospital Center.

Recruitment will end when approximately 40 participants are enrolled. It is expected that approximately 40 participants will be enrolled in order to produce 40 evaluable participants.

5.7 Participant Withdrawal or Termination

5.7.1 Reasons for Withdrawal or Termination

Participants are free to withdraw from participation in the study at any time upon request. An investigator may terminate participation in the study if:

- Any clinical adverse event (AE), laboratory abnormality, or other medical condition or situation occurs such that continued participation in the study would not be in the best interest of the participant
- The participant meets an exclusion criterion (either newly developed or not previously recognized) that precludes further study participation

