5.2 Exclusion Criteria

An individual who meets any of the following criteria will be excluded from participation in this study:

1. Any patient with a traumatic open wound (only surgically created wounds will be included)
2. History of chronic pain
3. History of narcotic addiction
4. History of recreational drug dependency
5. History of psychiatric pathology
6. Allergy to local anesthetics, recombinant human thrombin or tranexamic acid
7. Any patient receiving a supra/infraclavicular block for anesthesia

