6.1.3 Route of Administration

Study drugs are applied topically to surgical bed prior to closure of skin.

7 Study Procedures and Schedule

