- The patients will be counseled on the study objectives and methods of data collection. The numerical pain rating scale will be explained in detail to the patient.
- The patients will be administered a pain diary in which they will be able to log their daily pain level at the same time each day (AM) based on the numeric pain scale (1-10). They will also be instructed to log their pain medication usage and the number of pills of Norco 5/325 mg that are consumed. This log will continue daily for a total of 14 days postoperatively.

The first visit will be the initial evaluation of the patient when they present for their individual hand surgery evaluation. If they qualify for their study, an initial preoperative pain scale will be used to assess their pain level.

The next assessment will be on the day of surgery. The patient will be evaluated in the preoperative holding area and another pain level evaluation will be done for a POD#0 timepoint.

The patient will be evaluated in PACU for total time in PACU.

Each patient will receive their log book and take it home with them. The patients will be called on each day by the study team to ensure that they have been logging their daily pain score. The study team will call the patient for this purpose.

The patients will be seen in person on their first postoperative visit (approximately 1-2 weeks later). If this is prior to postoperative day 14, they will follow up again in hand clinic after day 14 (in 4-6 weeks post-surgery) to submit their log books.

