8.3 Time Period and Frequency for Event Assessment and Follow-Up

The occurrence of an AE or SAE may come to the attention of study personnel during study visits and interviews of a study participant presenting for medical care, or upon review by a study monitor. All AEs including local and systemic reactions not meeting the criteria for SAEs will be captured on the appropriate RF. Information to be collected includes event description, time of onset, clinician's assessment of severity, relationship to study product (assessed only by those with the training and authority to make a diagnosis), and time of resolution/stabilization of the event. All AEs occurring while on study must be documented appropriately regardless of relationship. All AEs will be followed to adequate resolution.

Any medical condition that is present at the time that the participant is screened will be considered as baseline and not reported as an AE. However, if the study participant's condition deteriorates at any time during the study, it will be recorded as an AE. UPs will be recorded in the data collection system throughout the study.

Changes in the severity of an AE will be documented to allow an assessment of the duration of the event at each level of severity to be performed. AEs characterized as intermittent require documentation of onset and duration of each episode.

The PI will record all reportable events with start dates occurring any time after informed consent is obtained until 7 (for non-serious AEs) or 30 days (for SAEs) after the last day of study participation. At each study visit, the investigator will inquire about the occurrence of AE/SAEs since the last visit. Events will be followed for outcome information until resolution or stabilization.

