10.1.2 Analysis of the Primary Efficacy Endpoint(s)

Data will be expressed either as a mean (SD) or median and interquartile range (IQR). To evaluate PACU time as a function of each group, a one way analysis of variance test followed by a Tukey-Kramer post hoc test will be performed. To assess the number of pain pills need as a function of each group, a Kruskal-Wallis test followed by a Dunn post hoc analysis will be performed. To compare pain levels between the treatment arms, pain scores on a scale of 1 (lowest aka no pain) to 10 (highest pain experienced in life) will be collected daily via a patient log. They will be analyzed as a change from baseline (preoperative) pain levels and analyzed used a series of two proportion z tests with a family error rate equal to 0.05. For all tests, a P value of less than 0.05 will be considered statistically significant.

Pain is a subjective measure. We will be using an analog pain scale and reference them to the patients pre and postoperatively to account for this. Patients may take over the counter pain medication postoperatively. We cannot control the patient's use of over the counter pain medications while at home, thus we will have to rely on their accuracy and honesty for this study.

Patients will be called daily to ensure completion of daily log books. If they are not able to do this, they will be removed from the study analysis. If the patients return to clinic at 4-6 weeks post-surgery and they have completed their logs, their data will still be accepted. But if there is missing data, they will be removed from the analysis.

11 Source Documents and Access to Source Data/Documents

All data will be stored on HIPAA compliant and encrypted REDCap, approved by the institution and managed by MCIT.

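### Section 5.7.1 does not separate ending treatment from ending follow-up, so a treated participant can leave the pain analysis and routine adverse-event recording for reasons related to outcome

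*Combined protocol and SAP*

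**What the plan says.** Section 5.7.1 says that the investigator may end a participant's time in the study on two grounds. The first is an adverse event, laboratory abnormality or other condition such that "continued participation in the study would not be in the best interest of the participant". The second is that "The participant meets an exclusion criterion (either newly developed or not previously recognized) that precludes further study participation". The section does not say whether diary and safety data are still collected afterwards.

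Four other sections decide what such a termination does:

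- Section 6.1.3: "Study drugs are applied topically to surgical bed prior to closure of skin". Exposure is a single intraoperative application.
- Section 7.1.1, on the pain diary: "This log will continue daily for a total of 14 days postoperatively".
- Section 10.1.2, on incomplete diaries: "But if there is missing data, they will be removed from the analysis". No intention-to-treat population is defined.
- Section 8.3: reportable events are recorded "until 7 (for non-serious AEs) or 30 days (for SAEs) after the last day of study participation". It also has unresolved events followed to resolution, and asks for possibly related later events to be notified to the sponsor without a time limit.

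Section 5.6 expects about 40 enrolled to give 40 evaluable.

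**The concern.** Once the wound is closed there is no study treatment left to stop. What remains is a diary, daily calls and routine visits, so ending participation removes no exposure and loses only information. The two grounds in 5.7.1 can both arise after treatment and because of it: an adverse event plainly can, and an allergic reaction could make a participant newly meet the criterion "Allergy to local anesthetics, recombinant human thrombin or tranexamic acid".

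Two things are at stake. First, through 10.1.2, a randomized and treated participant can drop out of the pain comparison for a reason connected with how they fared, which randomization does not protect against. Second, through 8.3, a participant who has already had a problem can be the one for whom new events are recorded for the shortest time. The halting rule in section 8.5 rests on a count of only three unexpected related events, so complete collection of new events matters.

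**Working it through.** **Route to data loss.** Section 5.7.1 by itself removes no data. The steps are:

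1. The investigator ends participation after the agent has been applied (5.7.1).
2. If this is before day 14 and the diary stops, the log is incomplete (7.1.1).
3. An incomplete log removes the participant from the analysis (10.1.2).

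A termination after a complete 14-day log removes nothing by this route.

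**Sample size.** The plan's total is consistent: 4 arms × 10 = 40. The 10 per arm cannot be reproduced, because no effect size, standard deviation, event rate or power is stated. One removal from an arm of 10 is 1/10 = 10%; the figure is approximate because simple randomization need not give exactly 10 per arm.

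To show scale only, assume a comparison of two means, two-sided 0.05, no multiplicity adjustment and a normal approximation. This is not the planned pain test, which is a series of two-proportion z tests. The difference detectable with 80% power is (1.960 + 0.842) × √(2/n):

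- n = 10: 1.25 SD
- n = 9: 1.32 SD
- n = 8: 1.40 SD

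Power for a 1.253 SD difference falls from 80% at n = 10 to 76% at n = 9 and 71% at n = 8.

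**Possible shift in an arm mean.** If k of 10 are removed and their mean pain differs from the rest by g points, the arm mean moves by (k/10) × g. With assumed values k = 1 to 2 and g = 2 to 4, this runs from (1/10) × 2 = 0.2 to (2/10) × 4 = 0.8 points. The documents give neither k nor g, nor the sign of g.

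**Safety cut-offs.** Section 8.3 gives last day of participation + 7 (non-serious) or + 30 (serious). Section 5.5 puts a completer's last day typically at 4-6 weeks, that is day 28-42. Section 7.2 releases participants from study duties once the log is returned, after day 14, so day 14 is shown as an alternative reading. Day 3 is an assumed termination day.

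| Last day of participation | Non-serious recorded to | Serious recorded to |
|---|---|---|
| Day 3 (assumed termination) | 3 + 7 = 10 | 3 + 30 = 33 |
| Day 14 (log return) | 14 + 7 = 21 | 14 + 30 = 44 |
| Day 28 | 28 + 7 = 35 | 28 + 30 = 58 |
| Day 42 | 42 + 7 = 49 | 42 + 30 = 72 |

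The 7 and the 30 cancel, so the gap for both kinds of event is the difference in last days: 28 − 3 = 25 to 42 − 3 = 39 days, or 14 − 3 = 11 days on the log-return reading. For termination anywhere from day 0 to day 7, against day 28-42, it is 28 − 7 = 21 to 42 − 0 = 42 days.

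**The case against.** The strongest reply is that 5.7.1 is a permission with limits. It says may; the adverse-event ground needs a best-interest judgement; and the exclusion ground needs a criterion that rules out further participation. If all that remains is a diary and routine visits, that test should rarely be met. The clause also has a proper use before surgery, since randomization can precede it by up to 3 months and eligibility is rechecked on the day. This stands: a reader might infer that participants who react are the ones who will be dropped, but the text shows only that they can be.

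Other points also stand in part:

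- The removal rule in 10.1.2 applies to anyone with missing diary data for any reason, so it is the main cause of data loss. Changing 5.7.1 alone would not cure it.
- The triggering event is followed to resolution, and possibly related later events are to be notified. What is lost is active questioning about new events at the remaining one or two visits. Notification that waits for someone to come forward is weaker than asking, but it is not nothing.
- A reader might infer that chronic pain or addiction ("History of narcotic addiction") arising after surgery would remove participants with poor outcomes. To cost diary data, either would have to be established within 14 days, which the documents do not suggest.
- A reader might infer that the allergy criterion removes participants in arms 2 and 3 but not arm 4, and so flatters those arms. The documents do not support this. Arm 4 also contains thrombin, every arm contains the local anesthetics, and the adverse-event ground applies to all arms.

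**Conclusion.** The point holds as a gap in the rules. Sections 5.7.1 and 10.1.2 together permit an outcome-related exclusion after randomization, and 5.7.1 with 8.3 shortens routine recording of new events for a treated participant whose participation is ended early.

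Each exclusion is about 10% of an arm in a plan with no attrition allowance. The loss of recording time is 25-39 days under the assumed day-3 termination and a completer's last day of 28-42, or 11 days if participation ends at log return on day 14.

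The size and direction of any bias are unknown: no termination rate is given, and nothing shows that those terminated would have more pain than the rest. The trial is single-blinded, and the documents do not say whether the person deciding on termination knows the arm. No arm-specific direction can be claimed. The only asymmetry is that the allergy criterion in section 5.2 names tranexamic acid but not aminocaproic acid, the added agent in arm 4.

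**What to change.** Three edits, none of which touches treatment or the investigator's clinical judgement:

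1. **Section 5.7.1.** State that once the agent has been applied, an adverse event or a newly met exclusion criterion does not by itself end data collection. Treated participants stay in diary, call and safety follow-up unless they withdraw consent, or the investigator documents that data collection itself is against their interest.
2. **Section 8.3.** Run the non-serious and serious event windows for every treated participant from one fixed point, such as the day of surgery or the scheduled final visit.
3. **Section 10.1.2.** Analyse all treated participants as randomized, using the diary data available, and state how a partial diary enters the pain comparison, in place of removal for an incomplete log.

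Separately, the allergy criterion in section 5.2 and the list of agents in section 6.1 need to be reconciled.

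The cost is a few sentences and slightly more analysis work. Some participants with protocol departures or partial diaries will remain in the data set.

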5.8 Premature Termination or Suspension of Study

This study may be temporarily suspended or prematurely terminated if there is sufficient reasonable cause. Written notification, documenting the reason for study suspension or termination, will be provided by the suspending or terminating party to study investigators and to regulatory authorities. If the study is prematurely terminated or suspended, the PI will promptly inform the IRB and will provide the reason(s) for the termination or suspension.

Circumstances that may warrant termination or suspension include, but are not limited to:

- Determination of unexpected, significant, or unacceptable risk to participants
- Demonstration of efficacy that would warrant stopping
- Insufficient compliance to protocol requirements
- Data that are not sufficiently complete and/or evaluable
- Determination of futility

Study may resume once concerns about safety, protocol compliance, data quality are addressed and satisfy the IRB.

6 Study Agent (Study drug, device, biologic, vaccine etc.) and/or Procedural Intervention

6.1 Study Agent(s) and Control Description

1. Topical lidocaine and bupivacaine alone
2. Topical lidocaine and bupivacaine with thrombin
3. Topical lidocaine and bupivacaine with thrombin and tranexamic acid
4. Topical lidocaine and bupivacaine with thrombin and aminocaproic acid

6.1.1 Acquisition

All drugs in this study are readily available at the hospitals where the study is to be performed. Nursing staff will verify expiration date and untampered vials prior to use intraoperatively. Unused drugs will be disposed of by all proper protocols per the hospital.

CONFIDENTIAL

This material is the property of the NYU School of Medicine and Langone Medical Center. Do not disclose or use except as authorized in writing by the study sponsor
Interventional Template Version: 11 January 2019

6.1.2 Dosing and Administration

Tranexemic acid:

We plan on using a total dose of 500 mg (20 mL) total for each case.

Aminocaproic acid: We will use a total of 1000 mg total for each case.

Recombinant Human Thrombin:

For our topical application, we will use a total of 10000 units per open surgical study arm involving use of Thrombin.

Lidocaine Hydrochloride with Epinephrine:

We plan on using a total of 5 mLs per open surgical study arm involving lidocaine hydrochloride and epinephrine.

Bupivacaine Hydrochloride with Epinephrine:

We plan on using a total of 5 mLs per open surgical study arm involving bupivacaine hydrochloride with epinephrine.

Each study arm will receive an intraoperative local block at the site of surgery by the operative surgeon prior to incision.

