Bupivacaine Hydrochloride with Epinephrine: We plan on using a total of 5 mLs per open surgical study arm involving bupivacaine hydrochloride with epinephrine.

Each study arm will receive an intraoperative local block at the site of surgery by the operative surgeon prior to incision, in accordance with our institutional standard of care..

2.3 **Rationale**

Pain management immediately post operatively is often difficult without utilizing opioids. With increasing concern about opioid addiction, our study hopes to elucidate other methods of immediate post operative pain control that will limit the amount of opioids taken after having elective hand surgery.

We propose that the utilization of thrombin, topical anesthetic, and an antifibrinolytic will improve post operative pain control.

2.4 **Potential Risks & Benefits**

2.4.1 **Known Potential Risks**

Lidocaine: Tinnitus, cardiac irritability, and neurological disturbance have been noted only when patients receive more than 4mg/kg of lidocaine. In this study, we are using less than 1mg/kg, which is a lot lower than the maximum amount of medication given to patients.

Bupivacaine: Tinnitus, headache, difficulty with urination, chest discomfort, problems with speech, cardiac irritability, and neurological disturbance have been noted only when patients receive more than 3mg/kg of bupivacaine. In this study, we are using less than 1mg/kg, which is a lot lower than the maximum amount of medication given to patients.

It is well known that bupivacaine can cause adverse effects (cardiotoxicity, and central nervous system toxicity); however, the dose and route of administration in our study minimizes these risks, as noted above.

Thrombin: Major risks of thrombin have only been seen in systemic usage. We are using thrombin only topically, in order to minimize side effects that may occur when used systemically. Topical thrombin per

CONFIDENTIAL

the FDA has risks of anaphylactic reactions that may occur in the clinical trial with similar frequency in the two study groups. The most common adverse event reported was procedural complications and pruritus. This risk is seen in patients with amide anesthetic sensitivity and we will screen patients for this preoperative and exclude patients with this potential risk.

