4.1 Description of Study Design

The study is a single blinded placebo-controlled prospective randomized controlled trial. Patients will be randomized into one of four groups:

1. Topical lidocaine and bupivacaine alone
2. Topical lidocaine and bupivacaine with thrombin
3. Topical lidocaine and bupivacaine with thrombin and tranexamic acid

CONFIDENTIAL

This material is the property of the NYU School of Medicine and Langone Medical Center. Do not disclose or use except as authorized in writing by the study sponsor
Interventional Template Version: 11 January 2019

4. Topical lidocaine and bupivacaine with thrombin and aminocaproic acid

Patients meeting inclusion criteria will be randomized at their preoperative appointments and an initial evaluation will be completed for pre-operative pain levels using the numerical pain rating scale. At the conclusion of their respective surgery just prior to wound closure, the appropriate medications will be topically administered into the wound and the wound will be closed via standard method. Patients will record pain scores at home daily and also record the amount of pain pills needed postoperatively until post operative day 14. Analysis will be completed to ascertain the difference between preoperative and postoperative scales after 14 days among the four groups. We will also analyze the differences in the amount of opioid pain pills needed postoperatively among the four study groups.

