5.4 Strategies for Recruitment and Retention

Patients will be prospectively recruited after IRB approval until a total of 10 patients are enrolled and randomized in each study group for a total of 40 patients. We believe this process will take approximately 2-3 months.

Patients will be recruited from investigator and sub-investigator clinical practices, during each patient's pre-operative visit for elective hand surgery.

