7.1 Study Procedures/Evaluations

7.1.1 Study Specific Procedures

Patients meeting inclusion criteria will be randomized at their preoperative appointments with a sealed envelope method and an initial evaluation will be completed for pre-operative pain levels using the numerical pain rating scale. At the conclusion of their respective surgery just prior to wound closure, the appropriate medications will be topically administered into the wound and the wound will be closed via standard method. Patients will record pain scores at home daily and also record the amount of pain pills (Norco 5/325mg) needed postoperatively until post operative day 14.

Preoperative analog pain scoring will be performed followed by postoperative analog pain scoring on postoperative day 0-14. Compliance will be recorded by the patient in a written form. Number of opioid pain medications taken will also be recorded by patient in a written form.

Analog pain scoring preoperatively on day of surgery and postoperatively day of surgery. Pain scale from 0 (no pain) to 10 (highest level of pain ever experienced). This scoring system will also be utilized by the patient daily until postoperative day 14.

Opioid prescriptions (Norco 5/325 mg) will be given to patients post operatively. Total number of pills taken up until post operative day 14 will be recorded by the patient.

This will allow us to track the patients relative pain pre and postoperatively until postoperative day 14.

- Medical history will be obtained in hand surgery clinic at initial patient presentation.

CONFIDENTIAL

This material is the property of the NYU School of Medicine and Langone Medical Center. Do not disclose or use except as authorized in writing by the study sponsor
Interventional Template Version: 11 January 2019

- Medication history will include details about the specifics of their hand problem along with a past medical history that includes history of chronic pain, narcotic addiction, recreational drug dependency, psychiatric pathologies, allergy to drugs and preferences for anesthesia. Those patients who only wish to have an anesthetic upper extremity block performed by anesthesia will not qualify for the study.
- Physical examination will consist of a full hand examination. The most important criteria will be the presence or absence of an already open wound prior to surgical intervention.

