7.2 Study Schedule

Screening/Baseline Visit (up to 3 months prior to day of surgery)

- Obtain informed consent of potential participant verified by signature on written informed consent for screening form.
- Review medical history to determine eligibility based on inclusion/exclusion criteria.
- Review medications history to determine eligibility based on inclusion/exclusion criteria.
- Perform medical examinations needed to determine eligibility based on inclusion/exclusion criteria.
- Schedule day of surgery where primary intervention will be performed.
- Provide participants with information regarding tranexamic acid, and operative steps for administration of drugs into surgical wound prior to closure.
- Provide participants with log books.
- Randomize patient using sealed envelope method.

Day of Surgery

- Verify patient still meets inclusion/exclusion criteria.
- Administer study treatment
- Patient fills out Day 1 of pain diary

Intermediate Visits

- Participants will be called via phone each day by the study team to ensure they have completed their daily log of numerical pain rating scale and number of pain pills taken.
- They will arrive for an intermediate visit on their first postoperative visit (variable time, between 3-14 days postoperatively). Log books will be collected only after postoperative day 14.

Final Study Visit (up to 6 weeks post surgery)

CONFIDENTIAL

This material is the property of the NYU School of Medicine and Langone Medical Center. Do not disclose or use except as authorized in writing by the study sponsor
Interventional Template Version: 11 January 2019

Pain logs will be collected from participants who have not already returned them to study staff. The participants will be released of their duties to the study once the log books have been returned to the physicians. They will continue their routine follow up per the follow up schedule for each hand surgery procedure. No additional data is collected for study purposes at post-op visits beyond data collected per standard of care.

8 Assessment of Safety

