10.1 Statistical and Analytical Plans (SAP)

10.1.1 General Approach

Each arm of this randomized, single-blinded, placebo-controlled study will have a minimum of 10 patients. There will be a minimum of 40 patients in the study. Patients will be randomized using Microsoft Excel.

Simple randomization will be used to determine the treatment arm. In order for us to power our study based on a previous similar study at NYU for topical application (Haddock et al., Thrombin and Topical Local Anesthetic for Postoperative Pain Management), we will need 10 patients for each individual treatment arm to detect any difference in the outcome.

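### The surgeon's pre-incision block follows allocation, its content is not specified or named as study data, and nothing keeps the surgeon unaware of the arm when giving it

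*Combined protocol and SAP*

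**What the plan says.** - **The block.** Section 6.1.2: "Each study arm will receive an intraoperative local block at the site of surgery by the operative surgeon prior to incision". Section 2.2.2 repeats the sentence and adds "in accordance with our institutional standard of care". Neither section, nor any other, gives the agent, concentration or volume.
- **Allocation.** Section 7.1.1: "Patients meeting inclusion criteria will be randomized at their preoperative appointments with a sealed envelope method". Section 7.2 lists "Randomize patient using sealed envelope method" under the screening/baseline visit, which may be up to 3 months before surgery. Neither says who opens the envelope, when, or who is told.
- **Blinding.** Section 4.1: "The study is a single blinded placebo-controlled prospective randomized controlled trial". The blinded party is not named.
- **Who operates.** Section 5.4: "Patients will be recruited from investigator and sub-investigator clinical practices". The operating surgeon may therefore be a member of the study team.
- **Data named for collection.** Pain scores and pill counts to day 14, adverse events, and, in section 7.1.1, "The patient will be evaluated in PACU for total time in PACU". The block is not among them. Section 11 makes the CRF the main data instrument but does not list its fields.
- **Analysis.** Section 10.1.2 compares arms on pain, pills and PACU time, with no term or table for the block, the surgeon or the procedure.

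**The concern.** The block is a co-intervention given after allocation and before the study solution, at the same site. The trial's hypothesis (section 2.2.1) is that a stable clot prolongs the local anesthetic effect, so a between-arm difference in local anesthetic is a direct rival explanation for a between-arm difference in outcome. Section 5.2 already excludes supra- and infraclavicular blocks, yet the one block that every patient receives is left open.

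If the surgeon knows the arm and infiltrates more generously in the local-anesthetic-only arm, a real benefit could be hidden. If the surgeon does so in an antifibrinolytic arm, a benefit could be created. This is separate from whether PACU, prescribing or telephone staff know the arm, because it acts before the study solution is applied.

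**Working it through.** **1. Order of events.** Randomisation is at the preoperative appointment (7.1.1, 7.2). The block is before incision (2.2.2, 6.1.2). The study solution goes in just before closure (7.1.1). Allocation therefore always comes before the block. No section closes the allocation to the surgeon in between.

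**2. Which outcomes.** The block agent is not named. If it is one of the trial's own anesthetics (an assumption), section 2.2.1 gives durations of 2 to 3.5 h for lidocaine and 2 to 9 h for bupivacaine. The direct effect would cover PACU time (a secondary endpoint, 4.2.2) and the first pain scores and pills. It would bear much less on a diary that runs to day 14.

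**3. The plan's own figure.** Section 10.1.1 states 10 per arm but gives no effect size, SD or power, so that number cannot be reproduced. For scale, 10 per arm gives 80% power at two-sided 0.05 for a difference of (1.960 + 0.842) × √(2/10) = 1.25 SD (normal approximation).

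**4. What a bias would do, if present.** PACU time is the outcome most exposed, and its planned pairwise method is Tukey-Kramer.
- Inputs: 4 arms and 10 per arm (10.1.1), familywise 0.05, error df = 40 − 4 = 36. The shift b, in SD units, is assumed; the documents give no block effect.
- Critical value: q(0.95; 4, 36) = 3.809, which on the t scale is 3.809/√2 = 2.693.
- Noncentrality: b/√(2/10) = 2.236 × b.
- Rejection probability for one pair with no drug effect: P(|T| > 2.693), with T noncentral t on 36 df.

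| Assumed shift b (SD) | Noncentrality | Per-pair false-positive rate |
|---|---|---|
| 0 | 0 | 1.1% |
| 0.25 | 0.559 | 2.3% |
| 0.5 | 1.118 | 6.9% |
| 0.75 | 1.677 | 17.1% |

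These rates take the pairwise test alone and do not require the overall ANOVA to be significant first. They do not carry over directly to the two-proportion z tests planned for pain or the Dunn comparisons planned for pills.

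**5. Bias against chance.** Section 10.1.1 says "Simple randomization will be used to determine the treatment arm". Suppose half of patients got a stronger block unrelated to arm (assumed). With X₁ and X₂ independent binomial(10, 0.5), P(|X₁ − X₂| ≥ 3) = 26% and P(|X₁ − X₂| ≥ 4) = 11.5%. Imbalance of that kind is ordinary noise that the test level already covers. Only a block that varies with the arm inflates the error rate.

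**The case against.** The strongest reply is that this is a chain of possibilities. Bias needs a surgeon who knows the arm and who also varies the block by arm. Sealed envelopes are specified, and nothing says the surgeon is told. Section 2.2.2 holds the block to one institutional standard in all arms. Any effect would be short-lived beside a 14-day diary. Keeping the surgeon unaware is also the general remedy for a single-blind design that does not name the blinded party. All of this stands as a limit on size and likelihood. It does not close the gap: the standard of care narrows variation without stating agent or volume, and no section says the envelope stays shut until the block is done.

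Three stronger readings are tempting, and the documents do not support them.
- A reader might infer that the block goes unrecorded and that unequal blocks could never be detected. The CRF fields are not shown, section 11 counts hospital records as source data, and routine operative records may hold the details. What can be said is that the block is not named as study data and no planned analysis would show a difference.
- A reader might infer that the surgeon does know the arm. The documents neither say so nor prevent it.
- A reader might quote the larger inflation from a single unadjusted two-sample t-test (df 18, two-sided 0.05): 8.3%, 18.5% and 35.5% at the same three shifts, from 5%. Section 10.1.2 does not plan that test; it plans Tukey-Kramer for PACU time and a family error rate for the pain tests.

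**Conclusion.** The point holds as an open route to bias, not as a demonstrated bias. What the text establishes is that allocation precedes a surgeon-given block, that the block's content is unspecified beyond standard of care, that block data are not named for collection, and that nothing keeps the surgeon unaware at that moment. The consequence rests on two assumptions the documents do not settle: that the surgeon knows the arm, and that blocks then differ by arm. The restriction to PACU time and early pain and pills rests on a third, that the block uses the trial's anesthetics. The rise from 1.1% to between 2.3% and 17.1% shows scale under assumed shifts and is not a forecast. The change is worth making because it closes the route cheaply.

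**What to change.** 1. In 6.1.2, 7.1.1 and 7.2, state that the allocation envelope stays sealed and is kept from the operating surgeon until the block has been given and the wound is ready for closure. Operating-room nursing staff, who already check the vials under 6.1.1, can hold it.
2. Add CRF fields for block agent, concentration, volume and time.
3. In 10.1.2, add a descriptive table of these fields by arm. Do not adjust for block volume in a primary or sensitivity analysis. It is measured after randomisation and may itself be affected by knowledge of the arm, so adjusting could add bias, and with 10 per arm it would be imprecise.

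The content of the block stays per institutional practice, and the sample size does not change.

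Cost: protocol wording, a few CRF fields and one table. The practical downside is that the study solution has to be prepared late in the case.
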